In our subsequent YELLOW II study, all patients with obstructive NTL received high-dose statin therapy for 8-12 weeks (22). The aim of the study was to characterize the relationship between the changes in plaque morphology assessed by NIRS/IVUS and OCT, HDL functionality and gene expression in peripheral blood mononuclear cells (PBMC) using microarray analysis. At the follow-up, we observed a significant increase in fibrous cap thickness (FCT) in the study lesion, enhancement of cholesterol efflux capacity (CEC) and significant perturbations of PBMC transcriptome in patients with stable coronary artery disease (CAD) treated with 40 mg rosuvastatin for 8-12 weeks. As a result, the prevalence of TCFA reduced from 20 to 7% (P=0.003) and there was a significant independent association between the thickening of the fibrous cap and improved CEC independent of lipid lowering and CRP reduction. In addition, we observed significant transcriptomic perturbations in genes related to cholesterol synthesis, regulation of fatty acid unsaturation, cellular cholesterol uptake, efflux and inflammation suggesting that several independent molecular mechanisms might be responsible for the beneficial effects of statin on plaque morphology. The unique translational combination of multi-modality intravascular imaging with clinically relevant cellular biology and comprehensive transcriptomics represents a powerful approach to assessing the effects and mechanisms of the efficacy of different lipid-lowering therapies for stabilizing atherosclerotic plaques.

With OCT imaging, we observed an increase in FCT after intensive statin therapy only in a subset of the study patients. Traditionally, response to statins is measured by the changes in serum lipids, however, these changes do not predict the beneficial changes in FCT, therefore, it is important to distinguish statin responders from non-responders using non-invasive methods. In our recent analysis, YELLOW II transcriptomic data was used to predict whether a patient's FCT increased in response to statin therapy using machine learning models (23). One of the model used 18 genes and was able identify statin responders with an accuracy of 95.7%, sensitivity of 94.3% and specificity of 97.1%.

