Hypothesis. In the YELLOW III study, we hypothesize that LDL-C lowering with evolocumab 140 mg every 2 weeks will result in a significant increase in OCT-defined minimal FCT and reduction of plaque lipid content assessed by NIRS compared to baseline in patients with CAD undergoing percutaneous coronary intervention (PCI). In addition, we hypothesize that there is an association between the changes in patient's plaque characteristics and PBMC gene expression and lipid metabolites at the baseline, which would allow us to develop a predictive model for detecting subjects that demonstrate the greatest response regarding plaque morphology to PCSK9 inhibition therapy. YELLOW III will provide an additional contribution to the ongoing HYUGENS study due to its unique design combining intravascular imaging and transcriptomic based machine learning approach, which will allow to uncover molecular mechanisms responsible for the beneficial changes in atherosclerotic lesions of patients treated with evolocumab.

STUDY OBJECTIVES

The aim of the study is to assess the effect of evolocumab on coronary plaque morphology using intravascular imaging, NIRS/IVUS and OCT, and PBMC gene expression analysis in patients with stable CAD on maximally tolerated statin therapy.

Primary endpoints. The primary end-points are the changes from baseline to follow-up (follow-up value minus baseline value) in (1) the minimal FCT assessed by OCT and (2) NIRS maxLCBI4mm after 26 weeks of evolocumab.

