 Screening. Written informed consent must be obtained from all subjects before any study-specific procedures are performed. We will screen patients scheduled for elective coronary angiography and/or coronary artery stenting, who are receiving statin therapy for at least 4 weeks or with history of statin intolerance (should not exceed 20% of the total cohort) with acceptable LDL-C levels. Patients with nonobstructive lesion (30-50% stenosis) by angiography and lipid-rich plaque with lipid arc >90° and minimal fibrous cap thickness ≤ 120 µm detected by OCT will comprise the final study population. Women of childbearing potential will undergo urine pregnancy testing. If necessary, we may request serum pregnancy testing to confirm equivocal urine-based results.

- 2. PCI and baseline imaging. Culprit vessel PCI will be performed according to best current practice. During the same angiographic procedure baseline OCT and NIRS/IVUS imaging of the non-obstructive study lesion will be performed after administration of intra-coronary NTG. A total of 25ml of blood will be drawn from the sheath during angiography for transcriptomic profiling of PBMC (mRNA and miRNA), lipidomics and cytokine analyses. Patients will undergo assessment of lipid levels, CK-MB, Troponin I, liver function, CBC, and hsCRP.
- 3. **Study drug allocation.** All patients will receive subcutaneously administered evolocumab 140 mg every 2 weeks for 26 weeks in addition to statins. Evolocumab will be administered on day 1 (the day of the first treatment) and through week 26 with a personal injector or prefilled auto injector/pens.
- Clinical visits. Study visits will occur during screening (day 1), weeks 12 and 26 (time of follow-up procedure). Subjects must fast overnight when fasting lipid samples are to be obtained.
- 5. Follow up Procedure. The follow-up procedure will be scheduled 26 weeks after the baseline PCI and should occur within ±2 weeks of their specified date. First, routine angiography to check the previous stent will be performed, then, repeat NIRS/IVUS and OCT of the non-obstructive study lesion will be performed after administration of intra-coronary nitroglycerin. A total of 25ml of blood will be drawn

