from the sheath during angiography for transcriptomic profiling of PBMC (mRNA and miRNA), lipidomics and cytokine analyses.. All study patients will undergo repeat assessment of lipid levels, CK-MB, Troponin I, liver function, CBC, and hsCRP. Bivalirudin or Heparin will be used as anticoagulation as per standard PCI protocol. All patients will have repeat CK-MB and TnI levels measured at 6-8 hours and if in hospital, 16-24 hours post PCI, and thereafter if levels continue to rise

- 6. Post Follow-up. After the follow up procedure patients will be referred back to their primary care physician as is our usual practice. All further adjustment of lipid lowering and other medications will be at the discretion of the primary care physician. The treatment received after 26 weeks of evolocumab will be documented, and clinical telephone follow up will be performed at 30 days, 6 months and 1 year after the follow-up procedure
- 7. Data analysis. Off-line image analysis will be performed by the Mount Sinai Intravascular Imaging core laboratory, which will have no knowledge of patient clinical presentation and treatment.. Statistical and bioinformatics analyses will be performed by an independent biostatistician unaware of clinical data.

For predictive model construction, each patient will be identified as an evolocumab responder or non-responder depending on whether FCT increased or decreased after the treatment. Similar to our YELLOW II transcriptomic sub study (23), an elastic net regularized generalized linear model and K top scoring pair (KTSP) classifier model will be built using clinical variables and PBMC transcriptomic, lipidomics and cytokine analyses data to predict changes in FCT to ascertain whether a patient's FCT will increase in response to treatment. The transcriptomic data will be pre-processed to identify the

mechanism of missing data, and data imputations will be performed for non-ignorable missing data. The accuracy, sensitivity and specificity of both algorithms will be evaluated in order to select the highest performing model. We believe that the predictive model might allow patients to have their FCT response approximated without undergoing intravascular imaging.

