- Men or women aged 18 years or older at screening who signed written Informed Consent
- Patients with coronary artery disease undergoing cardiac catheterization and PCI for a culprit lesion, who also have a non-obstructive study lesion (30-50% stenosis) identified by angiography in a non-culprit vessel.
- Patients with non-obstructive coronary artery disease and a 30-50% lesion identified by angiography
- Patients who are not candidates for PCI or CABG over the next 12 months, in the opinion of the investigator
- Patients treated with statins for at least 4 weeks with LDL-C level ≥ 80 mg/dL for low- or moderate -intensity statin use and ≥ 60 mg/dL for high-dose statin at screening (Table 3). Patients with history of statin intolerance and LDL-C ≥ 100 mg/dL.

- Angiographic criteria: 30-50% reduction of lumen diameter in addition to the target study lesion. The study segment should not have a history of percutaneous coronary intervention (PCI) or coronary artery bypass grafting (CABG), and may not be a bypass graft.
- OCT criteria: study lesion should have a lipid-rich plaque with lipid arc >90° and fibrous cap thickness ≤120 µm.
- Women of childbearing potential must agree to be on an acceptable method of birth control/contraceptive

Exclusion criteria:

- Patients who have acute myocardial infarction (Q wave or non-Q wave with CK-MB > 5 times above the upper normal (31.5 ng/ml) within 72 hours)
- Patients who are in cardiogenic shock
- Patients with left main disease or patients requiring coronary artery bypass graft surgery
- Patients with elevated CK-MB (>6.3 ng/ml) or Tnl (>0.5 ng/ml)
- Patients with platelet count < 100,000 cell/mm³
- Patients who have co-morbidity which reduces life expectancy to one year
- Patients who are currently participating in another investigational drug/device study
- Patients with liver disease
- Patient with creatinine > 2.0 mg/dL
- Pregnant women and women of childbearing potential who intend to have children during the duration of the trial
- Patients having undergone heart transplantation, or those that may undergo heart transplantation during the study period
- Patients with active autoimmune disease

Table 1. Timeframes for submission of safety data and aggregate reports to

Amgen

Safety Data	Timeframe for submission to	Send to
	Amgen	
Suspected Unexpected Serious	At time of regulatory submission	Amgen Safety
Adverse Reaction (SUSARs)		
Pregnancy/Lactation exposure	Within 1 business day of Sponsor	Amgen Safety

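### The response model pools clinical and omics predictors and compares only algorithms, so it cannot show whether baseline expression or lipid metabolites add anything beyond statin intensity and LDL-C

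*Combined protocol and SAP*

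**What the plan says.** - **Aim.** The Hypothesis paragraph proposes that "there is an association between the changes in patient's plaque characteristics and PBMC gene expression and lipid metabolites at the baseline", and that this would support a predictive model.
- **Model.** Study Procedures item 7 labels each patient a responder or non-responder "depending on whether FCT increased or decreased after the treatment". It then fits an elastic net and a K top scoring pair (KTSP) classifier "using clinical variables and PBMC transcriptomic, lipidomics and cytokine analyses data to predict changes in FCT". The clinical variables are not listed.
- **Comparison.** The only planned one is between the two algorithms: "The accuracy, sensitivity and specificity of both algorithms will be evaluated in order to select the highest performing model".
- **Statin exposure.** The inclusion criteria admit "Patients treated with statins for at least 4 weeks with LDL-C level ≥ 80 mg/dL for low- or moderate -intensity statin use", patients on high-dose statin with LDL-C of at least 60 mg/dL, and patients with past statin intolerance and LDL-C of at least 100 mg/dL. Screening also admits patients "with history of statin intolerance (should not exceed 20% of the total cohort"). Table 3 defines the intensity categories.
- **Statins and expression.** The account of YELLOW II reports "significant perturbations of PBMC transcriptome in patients with stable coronary artery disease (CAD) treated with 40 mg rosuvastatin for 8-12 weeks", including genes for cholesterol synthesis, uptake, efflux and inflammation.

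The text contains no clinical-only model, no adjustment or stratification by statin intensity, and no test of the added value of omics.

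**The concern.** The aim concerns baseline expression and lipid metabolites, but the performance to be reported belongs to a pooled model. Good pooled performance would not say which block of predictors produced it.

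Statin exposure is the specific threat. It differs between patients by design and can leave a mark on PBMC expression. The LDL-C entry floors of 60, 80 and 100 mg/dL differ by statin group, so lipid features can mark the group too. If cap response to evolocumab also differs by statin group, transcripts or lipids that merely record the group will appear to predict response.

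Item 7 suggests that the model might stand in for intravascular imaging in judging response. Statin group and LDL-C are in the chart already, so the case for running the assays depends on what they add to those two.

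**Working it through.** The plan states no sample size, performance target or response rate for this model, so there is no figure to reproduce. The check has a reading part and an illustrative part.

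**1. What the planned metrics can separate.** Elastic net and KTSP draw on the same pool of predictors. A difference between them reflects the algorithm. Separating the contribution of omics needs two models that differ only in whether omics are included, and none is planned. The secondary endpoint of change in PBMC expression does not fill the gap, because it does not relate baseline expression to cap response.

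**2. How large false credit could be.** Inputs:
- n = 110: an assumption, taken from the last numbered DSMB review in item 8. It is not a stated sample size.
- Mix of intolerant, low/moderate and high intensity of 20/40/40: an assumption. Only the 20% cap is in the text, and the simulation puts the intolerant group at that maximum and treats it as taking no statin.
- 18 statin-sensitive genes shifted by 1.0, 0.4 and 0 SD in the three groups, with no link to response within a group: an assumption.
- Response rates by group and within-group gene correlation ρ: assumptions, varied below.

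The score is the mean of the 18 genes. Its within-group SD is √(ρ + (1−ρ)/18), which is 0.24 for ρ = 0, 0.58 for ρ = 0.3 and 0.73 for ρ = 0.5. Higher correlation leaves more noise around the same shift. False credit is the share of simulated trials in which the score is associated with response at p<0.05.

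| Response by group | ρ | AUC | False credit |
|---|---|---|---|
| Equal | 0 | 0.50 | about 5% |
| 85/75/65% | 0 | 0.59 | 31% |
| 85/75/65% | 0.3 / 0.5 | not tabulated | 15% / 11% |
| 90/75/60% | 0 | 0.63 | 58% to 60% |
| 90/75/60% | 0.3 / 0.5 | 0.58 / 0.57 | 25% / 19% |

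A repeat of the last row gave 21% to 27%. In the independent-gene scenarios with differing response, the average AUC within statin groups is 0.50, so the overall AUC there comes entirely from differences between groups.

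**3. What the benchmark does.** A second simulation used a single score tied more tightly to statin group (steps of 1 per group, noise SD 0.5), n of 110 or 140, and mixes of 20/40/40 or 10/30/60. Where response differed by group, from 80/75/65% to 90/80/50%, the score was significant alone in 18.4% to 94.7% of runs. With statin group in the model the figure was 5.2% to 6.1%. Over all scenarios, including equal response, it was 4.1% to 6.1%. The upper figures reflect the tight link and the steep gradient assumed, so they show what the remedy does and do not estimate the problem.

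**4. How this looks on the planned metrics.** With 90/75/60%, every group is above 50%. A classifier that knows only statin group and cuts at 0.5 calls everyone a responder:
- accuracy = 0.2×0.90 + 0.4×0.75 + 0.4×0.60 = 0.72
- sensitivity 100%, specificity 0%

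The AUC of statin group alone follows from its distribution among responders (0.18, 0.30, 0.24, each over 0.72 = 0.250, 0.417, 0.333) and non-responders (0.02, 0.10, 0.16, each over 0.28 = 0.071, 0.357, 0.571):
- AUC = 0.250×(0.357+0.571) + 0.417×0.571 + ½×(0.250×0.071 + 0.417×0.357 + 0.333×0.571) = 0.65

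**The case against.** **The premise may fail.** False credit needs cap response to differ by statin group, and the documents give no such rates. With equal rates the error is about 5%. The YELLOW II finding describes change after starting rosuvastatin 40 mg, not differences between background intensities. A history of intolerance need not mean no statin, since item 3 has evolocumab given on top of statins. All of this stands, and it is why the size is unknown.

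**The planned metrics would expose the pure artefact.** At a 0.5 cut-off, a model that only re-encodes statin group has near-zero specificity (step 4). This stands for that extreme case. A reader might infer that statin re-encoding alone would make the pooled model look impressive; the arithmetic does not support that. It does not rescue the plan, because no cut-off is stated, and a model with some real clinical signal could still have part of it attributed to omics.

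**Statin intensity may already be among the clinical variables.** It may, since they are not listed. Offering it to a penalised model does not settle attribution. In a small check (150 runs, n=110, 90/75/60%), an elastic net was given statin indicators beside 18 genes with no direct link to response. It returned a non-empty model in 75% of runs, and 94% of those kept at least one gene. Some of that is ordinary selection noise.

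**The hypothesis is one of association, not of increment.** A reader might infer that the expression hypothesis goes wholly untested. That is too strong: omics data enter the model, and a pooled predictor can be useful whatever drives it. What stands is narrower: the planned metrics cannot isolate the omics contribution.

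**Conclusion.** The gap holds and is worth closing before analysis. Item 7 compares algorithms on one pooled set of predictors, so its results cannot show whether baseline expression or lipid metabolites predict cap response beyond statin intensity and LDL-C. This follows from the text and needs no simulation.

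The size of any false credit is unknown. Under the assumptions shown it runs from about 5% (no difference in response by statin group), through about 10% to 27% (differing response, correlated genes), to about 60% (independent genes, 90/75/60%). The top figure should not be quoted alone. It needs independent genes, whereas genes in shared cholesterol pathways are plausibly co-regulated. The simulations also test a gene score and not the planned elastic net or KTSP.

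A reader might conclude that the transcripts are only statin markers. The documents do not show that; they show that the plan could not tell. The point concerns the predictive aim and touches neither primary endpoint.

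**What to change.** Prespecify, on the same resampling folds:
1. A clinical-only model with statin group (the two Table 3 categories plus intolerant), baseline LDL-C, age and sex.
2. A combined clinical-plus-omics elastic net with statin group left unpenalised.
3. As the reported result, the cross-validated gain in AUC and Brier score of the combined model over the clinical-only model, with a confidence interval.
4. KTSP performance against the same clinical-only model and within statin groups, because a pairwise-ranking rule has no direct counterpart to an unpenalised term.

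Do not use the 18-gene YELLOW II model as a benchmark. Its genes and parameters are not in the documents, and YELLOW II used microarray while the platform here is not stated.

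Item 7 also keeps the biostatistician blind to clinical data while the model uses clinical variables. The text should say how those variables, statin group included, reach the analysis.

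The cost is plan wording and one extra model fit, using statin and LDL-C data that eligibility already requires. The downside is that the apparent omics performance may look smaller.

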8. Safety reporting. Subjects will be carefully monitored during the study for possible Adverse Events (AEs) from the time of enrollment to the completion of their participation in the study. All adverse events will be fully investigated by the Principal Investigator, classified according to the current definitions of the International Organization for Standardization (ISO) and reported to the Mount Sinai Hospital IRB and Amgen Safety. Timeframes for submission of safety data and aggregate reports to Amgen are described in Tables 1 and 2.

In addition, an independent data and safety monitoring board (DSMB), comprising 3 cardiologists with extensive clinical research experience will oversee this study. The DSMB will be informed within 24 hours of all major adverse events (MACE) defined as a combined clinical endpoint of death, MI (Q wave or non Q-wave with CK-MB >3 times above the upper normal limit (48 U/L), urgent revascularization or stroke at 30 days and 1 year. All minor adverse events will be reported to the DSMB within 5 working days of knowledge of the event. The DSMB will convene after 30, 70 and 110 patients have completed the final procedure and at study closure. The DSMB will have complete discretion to adjudicate all events (major and minor), and, after fair deliberation and at any stage of the trial, to recommend the termination of the study, for whatever reason as they see fit insofar as it may pertain to adverse event occurrence(s). If the DSMB is to recommend termination of the study, the investigators will be given a single opportunity to respond to any concerns the DSMB may raise. After final consideration, if the DSMB again recommends termination of the study, then the study will be terminated. The DSMB may only terminate the study on the basis of MACE and adverse events.

9. Institutional Review Board (IRB). Prior to study initiation and when amended, the study protocol and will be submitted for review and approval to the Icahn School of Medicine at Mount Sinai IRB. Site personnel must provide reports of the progress, or completion, termination or discontinuation of the study to the institutional IRB at appropriate intervals. The primary investigator will verify that each subject has consented, in writing, to direct access to his/her original medical records for trial-related monitoring, audit, IRB/IEC review, and regulatory inspection

Inclusion criteria:

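### Does the FCT responder model need a written validation scheme and a deciding metric before the plan can stand?

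*Combined protocol and SAP*

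**What the plan says.** Under Study Procedures, item 7 (Data analysis), the outcome for the model is binary: "each patient will be identified as an evolocumab responder or non-responder depending on whether FCT increased or decreased after the treatment". Two candidate models are then named, with a pointer to earlier work: "Similar to our YELLOW II transcriptomic sub study (23), an elastic net regularized generalized linear model and K top scoring pair (KTSP) classifier model". Predictors are clinical variables plus transcriptomic, lipidomic and cytokine data. The whole of the evaluation plan is one sentence: "The accuracy, sensitivity and specificity of both algorithms will be evaluated in order to select the highest performing model". On missing data, the transcriptomic measurements are first examined for the mechanism of missingness, after which "data imputations will be performed for non-ignorable missing data".

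The purpose appears in two places. The Hypothesis paragraph expects an association between baseline molecular data and plaque change, "which would allow us to develop a predictive model for detecting subjects that demonstrate the greatest response regarding plaque morphology to PCSK9 inhibition therapy". Item 7 closes with a hope: "We believe that the predictive model might allow patients to have their FCT response approximated without undergoing intravascular imaging".

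The Primary endpoints are changes in minimal FCT and maxLCBI4mm. The Secondary endpoints paragraph lists imaging and gene-expression changes and mentions a search for predictive biomarkers. The classifier's accuracy is not listed as an endpoint.

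**The concern.** A classifier with far more candidate predictors than patients can separate responders from non-responders in its own training data even when nothing predicts response. If accuracy, sensitivity and specificity were computed on the patients used for fitting, a high figure would say little about performance in the next patient. The text available for this trial describes no split, cross-validation, bootstrap, hold-out set or external cohort.

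The second gap is separate. Picking the best model on three measures is not a complete rule, because sensitivity can favour one algorithm and specificity the other. The winner could then be settled after the results are known.

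A smaller point is that imputation is tied to one class of gap in one data type. Other transcriptomic gaps, and gaps in the clinical, lipidomic and cytokine predictors, have no rule.

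At stake is the credibility of a published accuracy figure for a tool that the authors hope could spare patients intravascular imaging.

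**Working it through.** **1. What the text commits to.** Item 7 names the outcome, the two algorithms, the predictors and three performance measures. It does not say that scoring uses the fitting data, and it does not say that it does not. The link to the earlier sub-study (reference 23) may carry a validation procedure. The word validation appears in that reference's title, but the title concerns the earlier statin model and its method is not shown, so it settles nothing either way. The accurate statement is that the procedure is not written out, not that none is planned.

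**2. Is there a plan figure to reproduce?** Not for this trial's model. For the earlier model, the section on YELLOW I and II gives accuracy 95.7%, sensitivity 94.3% and specificity 97.1%. Accuracy = p × sensitivity + (1 − p) × specificity, so the responder fraction is p = (97.1 − 95.7)/(97.1 − 94.3) = 1.4/2.8 = 0.50. The three figures agree with one another. No denominators or evaluation data are given, so they do not show how that model was scored.

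**3. Can the three measures disagree?** Yes. Take two assumed models: A with sensitivity 90% and specificity 70%, and B with 75% and 90%.

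- At 50% responders, A scores 0.5 × 90 + 0.5 × 70 = 80.0% and B scores 0.5 × 75 + 0.5 × 90 = 82.5%.
- At 70% responders, A scores 0.7 × 90 + 0.3 × 70 = 84.0% and B scores 0.7 × 75 + 0.3 × 90 = 79.5%.
- The ranking flips where 0.15p = 0.20(1 − p), that is p = 0.20/0.35 = 57.1%.

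The accuracy gaps are 2.5 and 4.5 points. The available text gives no total sample size. The safety section says "The DSMB will convene after 30, 70 and 110 patients have completed the final procedure and at study closure", which suggests at least 110 completers. With n = 110 assumed, the standard error of a single accuracy near 80% is √(0.80 × 0.20/110) = 3.8 points. In this example the choice turns on differences of about that size.

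In simulations with clean 10-fold cross-validation, sensitivity and specificity favoured different algorithms in 15 to 35% of runs with real signal. The rates on noise were higher (63 to 72%, and 100% at an assumed 70:30 class split), but there neither model works and the choice between them hardly matters.

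**4. How bad would scoring on the fitting data be?** Assumed inputs: pure noise, independent predictors, no gene pre-screen, 50% responders.

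| Setting | KTSP, fitting data | Elastic net, fitting data | Cross-validated |
|---|---|---|---|
| n = 110, 300 predictors, 9 pairs, fixed penalty | 87% | 83% | 51% and 50% |
| n = 70, 1,000 then 2,000 predictors, 9 pairs, tuned penalty | 95.4%, 96.9% | 64.1%, 68.4% | 48 to 51% |
| n = 110, 1,000 then 2,000 predictors, 9 pairs, tuned penalty | 90.5%, 91.6% | 62.5%, 66.3% | 48 to 51% |

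With 3 pairs instead of 9, KTSP falls to 87 to 88% (n = 70) and 80 to 82% (n = 110). Elastic net shifts by about 15 points or more between the first row and the others, according to settings the plan does not fix. Ordinary cross-validation removes the optimism. Reporting the better of the two cross-validated figures leaves about 54% where 50% is true, roughly 4 points.

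**5. Would a prescribed selection rule choose better?** With 1,000 predictors and real signal (20 predictors at 0.5 SD, or 5 at 0.8 SD), the accuracy of the chosen model on 2,000 new patients was:

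| Signal, n | Chosen on fitting data | Chosen by inner-fold balanced accuracy | Difference | Weaker model picked (fitting data v inner fold) |
|---|---|---|---|---|
| 20 at 0.5 SD, 70 | 63.2% | 62.7% | −0.5 | 35% v 39% |
| 20 at 0.5 SD, 110 | 70.4% | 69.2% | −1.2 | 2% v 23% |
| 5 at 0.8 SD, 70 | 65.8% | 66.4% | +0.6 | 33% v 28% |
| 5 at 0.8 SD, 110 | 71.2% | 73.2% | +2.0 | 19% v 2% |

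The stricter rule does worse in two settings and better in two. What validation improves is the honesty of the reported figure, not the choice of algorithm.

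**The case for a change.** The strongest opposing case is that the model is more than an afterthought. It appears in the study hypothesis, it is offered as a possible substitute for imaging, and the 95.7% reported for the earlier model invites a similar headline. The responder fraction is unknown until follow-up, so a deciding metric chosen then is chosen with the results in view. That gap remains whatever the cited sub-study contains. The reference is attached to building the models, and the plan restates no validation step.

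Much of this stands as description. The text is silent on both points. KTSP scores on fitting data are uninformative: with 1,000 predictors and 9 pairs they came out near 95% at n = 70 and 91% at n = 110, with or without signal.

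It does not amount to a defect in a stated rule. The alarming percentages need an analyst to score models on their own training data, which the plan does not propose. The same conclusion is not shown for tuned elastic net, which averaged 63 to 68% on noise and kept no predictor in 53 to 61% of the 50:50 noise runs. Balanced accuracy as the deciding measure, or elastic net as the default on a tie, would be a preference rather than a correction. On imputation, the plan looks at the missingness mechanism first. The uncovered gaps are unstated detail, and imposing missing at random by default would be a different choice, not a repair.

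**Conclusion.** No change to the plan is needed. This is a gap in detail that analysts building such classifiers would ordinarily fill with cross-validation, possibly by the procedure of the cited sub-study. It is not a wrong rule that has to be replaced. The primary endpoints and the listed secondary endpoints are unaffected, no treatment or stopping decision uses the model, and the plan's claim for it is tentative.

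The consequence depends wholly on conduct. With cross-validation around the whole fit, models built on noise score 48 to 51%, with about 4 points of optimism if the better of two is reported. Without it, nine-pair KTSP could show 87 to 97% on noise. These figures rest on assumed sample sizes (70 and 110), predictor counts, pair numbers, class splits and independent predictors, so they are not a magnitude for this trial. The missing tie-break matters only when the measures conflict (15 to 35% of simulated runs with signal), and the one selection rule tested changed accuracy in new patients by between −1.2 and +2.0 points. When results appear, a reader should look for which patients produced the performance figures; that is a matter for reporting.

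This conclusion would change if the plan, or the procedure it cites, were shown to report performance on the fitting data alone.
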